#### 8.3. Variables

The primary variable is the first recording (date) with tofacitinib for the treatment of ulcerative colitis (ICD-10: K51). Additional variables to be collected according to the list in Table 1.

## **Table 1. Variables Collected in This Study**

Data source for all variables is the eDMT based on patient charts.

Variable	Role	Operational definition
Tofacitinib start date	Index Inclusion criteria 1 Exclusion criteria 2	First day on tofacitinib administration
Date of birth	Exclusion criteria 1 Primary objective 7.2.1.a	Age will be defined as of index date
History of bowel surgery	Exclusion criteria 4	Panproctocolectomy, IPAA or ileostomy
Gender	Primary objective 7.2.1.a	Male/female
Smoking status	Primary objective 7.2.1.a	Current/ex-smoker/non- smoker/unknown
BMI	Primary objective 7.2.1.a	Derived from weight and height
Weight	Primary objective 7.2.1.a	kg
Height	Primary objective 7.2.1.a	cm
Treating hospital	Primary objective 7.2.1.a	name of treating hospital
Mayo score	Primary objective 7.2.1.c Secondary objectives 7.3.1.b, 7.3.1.c, 7.3.1.d, 7.3.1.e, 7.3.1.f, 7.3.1.i, 7.3.1.j, 7.3.1.k, 7.3.1.l, 7.3.1.o, 7.3.1.p.	Sum of "endoscopic findings", "stool frequency", Doctors assessment of disease severity" and "rectal bleeding"
First UC diagnose	Primary objective 7.2.1.b Inclusion criteria 2	Date
Extent of colonic involvement	Primary objective 7.2.1.b	Montreal classification: E1, E2 or E3
Endoscopic findings	Primary objective 7.2.1.c and 7.2.1.e. Secondary objective 7.3.1.m	0-3 (mayo score component)
Histological activity	Primary objective 7.2.1.e Secondary objective 7.3.1.n	Active disease (2) / inactive disease (1) /normal histology (0) / not determined
Clinician's assessment of disease severity	Primary objective 7.2.1.c	0-3 (mayo score component)

Variable	Role	Operational definition
Stool frequency	Primary objective 7.2.1.c Secondary objectives 7.3.1.r	0-3 (mayo score component)
Rectal bleeding	Primary objective 7.2.1.c Secondary objective 7.3.1.s	0-3 (mayo score component)
Fecal calprotectin	Primary objective 7.2.1.d, Secondary objectives 7.3.1.g and 7.3.1.h.	mg/kg
Plasma CRP	Primary objective 7.2.1.d Secondary objective 7.3.1.t	mg/L
Blood hemoglobin	Primary objective 7.2.1.d, Secondary objective 7.3.1.u	g/L
Blood leukocytes	Primary objective 7.2.1.d Secondary objective 7.3.1.v	cells/L
Blood thrombocytes	Primary objective 7.2.1.d Secondary objective 7.3.1.w	cells/L
Blood lymphocytes	Primary objective 7.2.1.d Secondary objective 7.3.1.x	cells/L
Blood neutrophiles	Primary objective 7.2.1.d Secondary objective 7.3.1.y	cells/L
Plasma albumin	Primary objective 7.2.1.d Secondary objective 7.3.1.z	g/L
Tofacitinib dose	Secondary objectives 7.3.1.a, 7.3.1.aa and 7.3.1.bb	mg*times/per day or "not on treatment"
Colectomies	Secondary objective 7.3.1.cc	Date
Type of healthcare contact	Secondary objective 7.3.1.cc	outpatient visit, remote contact, emergency visit or hospitalization
Prior IBD treatments	Secondary objective 7.3.2	Yes/no (For each treatment)
• corticosteroids		
• 5-aminosalicylic acid (5-ASA)		

Variable	Role	Operational definition
• azathioprine		
6-mercaptopurine		
• methotrexate		
• cyclosporine		
• ustekinumab		
• vedolizumab		
adalimumab		
• infliximab		
• golimumab		
Concomitant medications	Secondary objective 7.3.1.q,	product & dose
• corticosteroids		
• 5-ASA		
Extraintestinal manifestations: arthralgia, arthritis, sacroiliitis, pyoderma gangrenosum, erythema nodosum, primary sclerosing cholangitis, uveitis, ankylosing spondylitis, aphthous stomatitis, psoriasis	CCI	Yes/no per pre-specified list
Prior diagnoses	CCI	Yes/no per pre-specified list
Death date or lost to follow up	Used to define end of follow up	Date

Detailed definitions of variables and their analysis is available in the statistical analysis plan (SAP).

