7 STATISTICAL METHODOLOGY AND STATISTICAL ANALYSES

7.1 STATISTICAL METHODS

General:

Means, medians, and standard deviations, and 25% and 75% quartiles will be provided for continuous variables when performing descriptive analysis of continuous data. Numbers and percentages will be provided for dichotomous and polychotomous variables when performing descriptive analysis of categorical data.

Serial measures collected will be handled by "carry forward imputation", i.e. the latest value will be assumed unchanged until otherwise proven. Thus for each timepoint, the latest available measure will be used. Patients will be censored from the study post the last available contact/data entry. Missing values will not be imputed.

An unadjusted Kaplan Meier curve will be drawn to illustrate time-to-event and to estimate medians for time-to-event outcomes.

All data analysis will be executed using R, a language and environment for statistical computing and graphics, version 4.0.3 or later in Rstudio environment.

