7.2 STATISTICAL ANALYSES

Primary objectives a-e:

Describe the patient population at the baseline (initiation of tofacitinib), using the data collected. For each continuous variables (age, BMI, age at diagnosis, duration of disease, laboratory measures), provide the mean, median, sd, 25%Q and 75%Q values. For categorical variables (sex, smoking status, extent of colonic involvement, disease severity, endoscopic findings), report the number of patients, and proportion. Report proportion of missing values if present.

Secondary objective - Assess the Real-world Effectiveness of Tofacitinib

Secondary objective a:

For each patient, define the "on treatment" as Yes/No based on the latest available dose (at each timepoint 8, 16, 24 and 52 weeks). Patients marked with "not on treatment" prior to timepoint will be regarded as discontinued.

Report the proportion of patients on treatment, not censored at each timepoint.

Secondary objectives b, c, d, e, g, n:

For each patient, define the fulfilment of the remission/response criteria as Yes/No based on the latest available data (at each timepoint 8, 16, 24 and 52 weeks).

Report the proportion of patients on fulfilling the response/remission criteria, not censored at each timepoint.

Secondary objective f:

Define the time of response for each patient as first ever data-entry that fulfils response criteria. Fit competing-risk time-to-event model to the data, with time-to-event defined as time from index until response (event) or discontinuation (competing event), or end of data collection (censoring event).

Assess the cumulative incidence as function of time for both types of events. Illustrate the Aalen-Johansen state probabilities of multistate model.

Secondary objective h:

Select only patients with baseline f-calprotectin above 250 mg/kg at baseline. For each subsequent f-calprotectin measure, define below 250 mg/kg as Yes/No variable. Additionally, estimate the absolute delta change per baseline value.

For each timepoint (week 8, 16, 24 and 52), report the proportion of patients on fulfilling the <250mg/kg criteria, and summary statistics (mean, median, sd, 25%Q and 75%Q) of delta change, among patients not censored at each timepoint.

Secondary objectives i, j, k, m, o:

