For each subsequent visit, define the higher (10mg) dosing as Yes/No variable. For each timepoint (week 8, 16, 24 and 52), report the proportion of patients, among patients not censored at each timepoint.

Secondary objective cc:

Create composite endpoint of drug discontinuation, colectomy or UC-hospitalization, with time of the event as earliest of the aforementioned. Analyse time to event using Kaplan-Meier fit, where time to event is defined as time from index until composite endpoint (event) or time of data collection (censoring event).

Plot the Kaplan-Meier fit with the 95% CI and report the median survival if reached.

Secondary objective - Assess Treatment Lines Prior to Tofacitinib Treatment

Secondary objective a:

Summarize and tabulate types of previous UC treatments. Report N and proportion of patients that had corresponding treatment recorded.

Report the summary statistics (mean, median, sd, 25%Q and 75%Q) of number of treatments prior to tofacitinib if feasible.

NA

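### The date tofacitinib is stopped is neither listed for collection nor defined, although persistence, time to response (f) and the composite (cc) all need it

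*Protocol*

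**What the plan says.** Protocol Table 1, repeated in SAP section 2.1, defines the tofacitinib start date as "First day on tofacitinib administration". It also asks for dates of first UC diagnosis, colectomy, and death or loss to follow-up; the colectomy row reads "Colectomies Secondary objective 7.3.1.cc Date". There is no row for a tofacitinib stop date. The dose row holds "mg*times/per day or 'not on treatment" and is assigned to objectives a, aa and bb, not to f or cc.

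SAP 7.1 handles serial measures by carry-forward: "the latest value will be assumed unchanged until otherwise proven". For objective a, SAP 7.2 first sets on-treatment status from the latest available dose. It then adds: "Patients marked with 'not on treatment' prior to timepoint will be regarded as discontinued". For objective bb it works by contact: "For each subsequent visit, define the higher (10mg) dosing as Yes/No variable".

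Three analyses need a time of discontinuation:

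- the persistence analysis by Kaplan-Meier and/or Cox model (Protocol 8.7);
- objective f, where discontinuation is the competing event (SAP 7.2);
- objective cc: "Create composite endpoint of drug discontinuation, colectomy or UC-hospitalization, with time of the event as earliest of the aforementioned".

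SAP 7.1 censors patients at the last contact or data entry. For cc, SAP 7.2 censors at the time of data collection.

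**The concern.** An entry showing that a patient is off the drug cannot precede the stop. If that entry supplies the event date, every dating error is late and none is early. Kaplan-Meier persistence and cc are then shifted upward. In f the cumulative incidence of discontinuation at a given time is too low, and a response recorded after the true stop but before the off-treatment entry counts as a response on treatment. This error is systematic, so confidence intervals do not show it.

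Two further rules are unreconciled. The two objective-a sentences classify a patient who paused and restarted differently: the latest dose says on treatment, the earlier mark says discontinued. And if cc is censored at data collection, a patient who stops after the last contact counts as event-free up to that date.

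**Working it through.** The plan states no persistence figure to reproduce, so the check asks how large the error would be if the first off-treatment entry is the event date. Three inputs are assumptions not in the documents: a constant stopping hazard, true week-52 persistence S of 40-70%, and the gap g between contacts.

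**1. Irregular contacts every g weeks.** The last contact before week t lies uniformly 0 to g weeks earlier, so for t ≥ g

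observed S(t) = true S(t) × (e^(λg) − 1)/(λg), with λ = −ln S(52)/52.

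Example with S(52) = 50% and g = 13: λ = 0.6931/52 = 0.01333, λg = 0.1733, factor = 0.1892/0.1733 = 1.092, observed 54.6%, bias +4.6 points. The median moves by ln(1.092)/λ = 6.6 weeks, about g/2.

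| Gap (weeks) | Bias at week 52, S = 40% | 50% | 60% | 70% | Median late by (weeks, S = 50%) |
|---|---|---|---|---|---|
| 4 | +1.4 | +1.4 | +1.2 | +1.0 | 2.0 |
| 8 | +3.0 | +2.8 | +2.4 | +2.0 | 4.0 |
| 13 | +5.0 | +4.6 | +4.0 | +3.2 | 6.6 |
| 26 | +10.7 | +9.8 | +8.4 | +6.6 | 13.4 |

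A simulation of 400,000 patients agrees to within 0.2 points. Earlier timepoints are worse: with S = 50%, the simulated week-24 bias is +2.0, +4.0, +6.7 and +14.2 points for the four gaps.

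**2. Contacts only near weeks 8, 16, 24 and 52 (each ±3 weeks), hazard starting after week 8.** Half the patients have their week-52 contact before week 52, on average at week 50.5, which is 42.5 weeks after week 8. The other half still carry their week-24 status, 16 weeks after week 8. With S = 60%: λ = 0.5108/44 = 0.01161; e^(−0.01161×42.5) = 61.1%; e^(−0.01161×16) = 83.0%; mean 72.0%, bias +12. The same steps give 79.3% for a true 70% (+9) and 64.5% for a true 50% (+14).

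**3. A contact exactly at each timepoint.** The objective-a proportions have no bias. The Kaplan-Meier median can still be late: 52 against a true 39.3 weeks at S = 40%, and 78 against 70.6 at S = 60% (contacts at weeks 78 and 104 added).

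**4. Composite cc.** Suppose undated stops are 60-100% of first events and true event-free survival at week 52 is 50% or 60%. The simulated bias is +1.5 to +2.7 points with 8-week gaps and +4.8 to +9.8 with 26-week gaps.

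**5. The opposite direction.** If a share q of patients on the drug at week 52 had an earlier pause marked, the prior-mark rule reports S × (1 − q). With q = 5% and S = 40% this is 38% (−2 points); with q = 10% and S = 70% it is 63% (−7 points).

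**Scale.** The 95% half-width at 50% is 1.96 × √(0.25/n): 9.8 points for n = 100 and 8.0 for n = 150.

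**The case against.** The electronic form is not in the documents; it was still to be designed. Table 1 is a variable list. It gives only units or scores for laboratory values and Mayo items, yet the SAP places these at weeks 8 to 52 and takes the first qualifying entry as the time of response, so entries must carry dates. A dose entry could equally carry the charted stop date. This stands: dating the stop at the next contact follows from carry-forward and the per-contact wording for bb, but no section states it. It does not remove the gap, because no rule makes the entry date the stop date.

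The size depends on the contact pattern. Table 1 lists outpatient, remote, emergency and inpatient contacts, so contacts need not follow the analysis timepoints. In step 2 of the working, adding contacts at weeks 38 and 66 cuts the bias to 5-7 points. Contacts every 12 weeks after week 24 give 2-3 points. Placing the week-52 contact in the three weeks up to week 52 gives about 1 point. This also stands, and is why a range is reported.

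A reader might infer that every discontinuation result is biased towards longer persistence. The documents do not support that. The prior-mark rule pulls objective a down, the bias in objective a vanishes when a contact falls at the timepoint, and separately dated colectomies dilute the error in cc.

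Finally, these are secondary, descriptive outputs, and the primary objective (baseline characteristics) is untouched. That limits the weight of the point but does not answer it.

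**Conclusion.** The point holds as a gap with a conditional consequence. The discontinuation date is not listed and its event time is not defined, while three planned analyses need it. If the first off-treatment entry is used, time to discontinuation is late by roughly half the contact interval. Week-52 persistence is then overstated by about 1-3 points with 4-8-week gaps, 3-5 with 13-week gaps and 7-11 with 26-week gaps. The upper end, 9-14 points, applies only if contacts cluster near weeks 8, 16, 24 and 52, and should not be read as the expected error. All these sizes rest on an assumed constant hazard and on contact gaps the documents do not give.

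The net direction for objective a is unknown, because the prior-mark rule could lower it by 2-7 points if 5-10% of continuing patients had paused. The conflicts between the two objective-a sentences and between the two censoring rules need no assumption: they are in the text. The change should be made; the primary objective does not depend on it.

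**What to change.** 1. Add tofacitinib stop and restart dates to Table 1 and the data collection form, taken from the charts, with interruption recorded separately from permanent stop. Use them in a, f, cc and the persistence analysis, and assign them to those objectives in Table 1.
2. Where no date is charted, define the event time as the first off-treatment entry and add a midpoint or interval-censored sensitivity analysis. Midpoint dating leaves about 0.3 points or less at week 52 for irregular gaps up to 26 weeks. If contacts fall only at weeks 8, 16, 24 and 52 it misplaces the median (38 against a true 52 weeks at S = 50%), so the interval-censored estimate is then needed.
3. Reconcile the two objective-a sentences in SAP 7.2 by classifying status on the date itself, which fits an objective about who is taking the drug at each timepoint.
4. Reconcile the cc censoring rule (time of data collection) with SAP 7.1 (last contact or data entry).

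Cost: one or two extra date fields for 100-150 charts already being read, plus SAP wording. Some dates will be missing, which is why step 2 is needed.

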- o. Proportion of patients in sustained steroid free remission (pMayo and full Mayo score) (for all patients and for those treated with corticosteroids at baseline) and endoscopic remission (sub score = 0), mucosal healing (sub score 0-1) or endoscopic response (sub score reduction from baseline of ≥1) from week 8 to week 16, 24 and 52.
- p. Comparison of response and remission (pMayo and full Mayo score) based on the extent of colonic involvement.
- q. Proportion of patients with corticosteroid tapering at weeks 8/16/24/52 and their tapering rates and doses.
- r. Proportion of patients with improvement in stool frequency sub score of 1 or more points and change from baseline in stool frequency sub score at week 8, 16, 24 and 52.

- s. Proportion of patients with improvement in rectal bleeding sub score of 1 or more points and change from baseline in rectal bleeding sub score at week 8, 16, 24 and 52.
- t. Proportion of patients reaching normal P-CRP levels (below 4mg/L) and change from baseline in P-CRP levels at week 8/16/24/52.
- u. Proportion of patients reaching normal B-hb levels (men: 134–167 g/L, women: 117–155 g/L) and change from baseline in B-hb levels at week 8/16/24/52.
- v. Proportion of patients reaching normal B-leuk levels (3.4-8.2 x 10^9/L) and change from baseline in B-leuk levels at week 8/16/24/52.
- w. Proportion of patients reaching normal B-Thromb (150–360 x 10^9/L) and change from baseline in B-Thromb levels at week 8/16/24/52.
- x. Proportion of patients reaching normal B-ly  $(1.3-3.6 \times 10^9/L)$  and change from baseline in B-ly levels at week 8/16/24/52.
- y. Proportion of patients reaching normal B-neutr (1.5-6.7 x 10^9/L) and change from baseline in B-neutr levels at week 8/16/24/52.
- z. Proportion of patients reaching normal P-alb (18-39 years: 36-48 g/L, 40-69 years: 36-45 g/L, 70 years and over: 34-45 g/L) and change from baseline in P-alb levels at week 8/16/24/52.
- aa. Proportion of patients with extended tofacitinib induction dose (additional 8 weeks with 10mg).
- bb. Real-world dosing of tofacitinib, eg, usage of a higher dose (10 mg) as maintenance therapy.
- cc. Survival without drug discontinuation, colectomy or UC-related hospitalization (using time to event analysis).

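### A patient who dies on tofacitinib counts as event-free in the survival endpoint (objective cc): death only ends follow-up, and no listed variable separates it from loss to follow-up

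*Protocol*

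**What the plan says.** Protocol Table 1 (section 8.3) lists "Death date or lost to follow up" as one row. Its role is "Used to define end of follow up" and its operational definition is a date, with no status or reason. The SAP's Table 1 repeats the row unchanged.

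Protocol 7.3.1.cc names the endpoint "Survival without drug discontinuation, colectomy or UC-related hospitalization (using time to event analysis". SAP 7.2 builds it as follows: "Create composite endpoint of drug discontinuation, colectomy or UC-hospitalization, with time of the event as earliest of the aforementioned". Time runs as "time from index until composite endpoint (event) or time of data collection (censoring event".

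The general rule in SAP 7.1 differs: "Patients will be censored from the study post the last available contact/data entry".

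The SAP's only working definition of discontinuation stands under objective a: "Patients marked with 'not on treatment' prior to timepoint will be regarded as discontinued".

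For time to response (objective f), time runs from index "until response (event) or discontinuation (competing event), or end of data collection (censoring event". Death appears nowhere in that list.

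Safety endpoints are not applicable (SAP 5.2), and none of the table shells in SAP 8 has a row for deaths.

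**The concern.** An endpoint labelled as survival without certain events is normally read as counting deaths, and this one does not. Ordinary Kaplan-Meier censoring treats a dead patient as someone who would have gone on with the same future risk as those still under observation. A death on drug then leaves the curve without lowering it, and the resulting error always favours the drug.

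In objective f, a dead patient can no longer respond, yet death is not among the competing events.

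Death is probably the most serious outcome that the study collects, and the plan gives it no place in any reported result.

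**Working it through.** The plan gives no figure to reproduce: Protocol 8.5 states that sample size calculations do not apply. The check has two parts.

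**1. Tracing a death through the rules.** Take a patient who dies on tofacitinib with no earlier not-on-treatment record, colectomy or UC hospitalization.

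| Rule | Treatment of this patient |
|---|---|
| Table 1, both documents | Date ends follow-up; same row as loss to follow-up |
| SAP 7.2, cc event | No component met, so no event |
| SAP 7.2, cc censoring | Event-free until time of data collection |
| SAP 7.1 censoring | Censored after last contact or data entry |
| SAP 7.2, f | Neither response nor competing event |

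The two censoring rules disagree about time, but neither makes the death an event. A patient with an earlier component event already counts in cc and is unaffected.

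**2. Size in cc.** Inputs: n = 100 to 150 (Protocol 8.2 and 8.5). Assumptions not in the documents: 50% event-free at week 52 apart from death, exponential event times so that S(t) = 0.5^(t/52), deaths uniform over weeks 8 to 52 among event-free patients, and no other censoring before week 52.

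*Literal cc rule.* The patient stays event-free past week 52. Counting the death as an event instead removes the patient's whole weight:
- overstatement per death = 1/n
- 1/100 = 1.0 point; 1/150 = 0.67 point

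*SAP 7.1 rule.* The patient is censored at death time d, and Kaplan-Meier passes the weight 1/n to those still at risk. The share S(52)/S(d) of it survives to week 52:
- overstatement per death = (1/n) × mean of S(52)/S(d)
- with u = (52 − d)/52, uniform from 0 to 44/52 = 0.846, the mean of 0.5^u is (1 − 0.5^0.846)/(0.846 × ln 2) = 0.444/0.587 = 0.76
- 0.76/100 = 0.76 point; 0.76/150 = 0.50 point

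Simulated Kaplan-Meier curves (800 runs per scenario, same assumptions) agree. Overstatement at week 52, in percentage points:

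| Deaths | n = 100, SAP 7.1 | n = 100, literal cc | n = 150, SAP 7.1 | n = 150, literal cc |
|---|---|---|---|---|
| 0 | 0 | 0 | 0 | 0 |
| 1 | 0.8 | 1.0 | 0.5 | 0.7 |
| 2 | 1.5 | 2.0 | 1.0 | 1.3 |
| 3 | 2.3 | 3.0 | 1.5 | 2.0 |
| 5 | 3.8 | 5.0 | 2.5 | 3.3 |

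The zero row follows by definition. If other patients are censored before the death, each remaining patient carries more weight than 1/n and the figures rise.

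**3. Direction in f.** Under SAP 7.1, the dead patient's weight passes to patients who can still respond, so the cumulative incidence of response is inflated. Under the literal f text, the patient stays in the risk set until end of data collection. With no earlier censoring, the estimate is then responders divided by n, the same as with death as a competing event. The error in that case is that the state-probability plot shows a dead patient as still awaiting response.

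**The case against.** **The form may hold two fields.** Table 1 lists variables, and the data-entry form (the eDMT) is not in the documents. Other single rows plainly cover several items, such as prior treatments and extraintestinal manifestations. A reader might infer that deaths cannot be counted, or that the gap cannot be repaired once data reach the analysis environment. The documents do not support either statement. They show only that the plan lists no variable separating the two outcomes. Two fields on the form would still leave death without a role in cc and f.

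**Death might be taken as discontinuation.** The not-on-treatment rule is written under objective a, neither cc nor f defines discontinuation, and chart review could yield such an entry after a death. If the analyst did this, cc would be right. It stands that the SAP is silent here. But the only definition it gives requires a record, and nothing says that a death creates one.

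**Response need not be inflated.** A reader might infer that death can only raise the cumulative incidence of response. That holds under SAP 7.1 but not under the literal f text.

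**The effect is small.** At 50% event-free, the 95% confidence half-width is 1.96 × √(0.25/100) = 9.8 points, or 1.96 × √(0.25/150) = 8.0 points, against 0.5 to 1.0 point per death. The study is descriptive, and there may be no deaths. This stands as a limit on size. It does not excuse an error that always goes in the favourable direction and is cheap to avoid.

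**Adding death changes the endpoint.** The SAP composite matches the protocol objective, and Protocol 8.7 speaks of persistence of treatment. This also stands: the change adds a component and should be declared as one.

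**Conclusion.** The concern holds in this form: as written, a death on drug without an earlier component event adds no event to cc, and event-free survival is overstated under either censoring rule. Per death, the size is about 0.5 to 0.8 points with SAP 7.1 censoring and about 0.7 to 1.0 points on the literal cc text, for n = 150 and n = 100 respectively. These figures rest on 50% event-free at week 52, exponential event times, deaths spread evenly over weeks 8 to 52, and no other early censoring. The total depends on the number of deaths, which the documents do not give and which may be zero.

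For f, the omission of death as a competing event is clear, but the direction of the error is settled only once the censoring rules in SAP 7.1 and 7.2 are reconciled.

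The numerical effect is likely to be modest. The case for acting rests mainly on the endpoint's label, the absence of any reported death count, and the low cost.

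**What to change.** - In the eDMT, record date of death separately from date lost to follow-up, or add a reason code to the single date. Make the same change in Table 1 of both documents.
- In SAP 7.2, count death from any cause as an event in cc and as a competing event in f. Keep loss to follow-up as censoring.
- Reconcile the censoring times in SAP 7.1, f and cc so that one rule applies.
- Report the number of deaths. Where the export rule in Protocol 8.6 applies, give it as fewer than 5.

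The cost is one field or code on the form, best added before data mining, and a few SAP sentences; no new data source is needed. The downsides are that event-free survival may be slightly lower and that cc gains a component that Protocol 7.3.1.cc does not list. Protocol 8.7 lets the SAP modify the protocol's plans and calls for an amendment only for major changes to primary endpoints. A declared change in the SAP therefore appears sufficient for this secondary objective.
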